Hypothesis 2: At 15-months, Veterans in the STEP-KOA group will maintain improvements in WOMAC scores achieved at 9 months (i.e. there will be no estimated mean difference in WOMAC scores between 9 and 15 months). We will estimate these differences in WOMAC scores for the full STEP-KOA group as well as for subgroups defined by the combination of steps received during the STEP-KOA program.

Specific Aim 3: To describe patients who are non-responders at each Step in the STEP-KOA group, and to examine patient characteristics associated with non-response.

Specific Aim 4: To examine the cost effectiveness of overall STEP-KOA intervention, compared with the AE control group.

This study will have an important impact for Veterans because it evaluates a novel, patient-centered approach to improving physical activity and related outcomes for knee OA – one of the most common and disabling health problems. The study will have an important impact for the VA because the STEP-KOA could be a practical approach for both improving access to physical activity interventions and targeting more costly and limited PT resources for knee OA in an evidence-based manner.

RESEARCH PLAN

A. BACKGROUND AND CONTEXT

1.0 Osteoarthritis (OA) is Highly Prevalent and Disabling.

Osteoarthritis is one of the most prevalent chronic conditions in the U.S. Knee OA is particularly common, with one study indicating a lifetime risk of 45%,^{1,2} and the prevalence of knee OA is expected to rise dramatically over the next several decades³. OA is associated with significant pain, functional limitations, and reduced health-related quality of life⁴. It is the most frequently reported cause of disability in the U.S.⁵. Among older adults, the risk of disability attributable to knee OA is as great as that due to cardiovascular disease and greater than any other medical condition⁶. OA is also associated with significant costs to both patients and health care systems. Annual health care expenditures of individuals with OA are about twice as high as individuals without OA, even when adjusting for age and gender⁷.

2.0 Osteoarthritis is a Particular Burden in Veterans.

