As described below, STEP-KOA begins with a low-resource intervention, involving access to an internet-based exercise program for knee OA (Step 1). Patients who do not meet response criteria for pain and function, established by the Outcome Measures in Rheumatology group and the Osteoarthritis Research Society International (OMERACT-OARSI³⁶), after Step 1 will progress to a more intensive intervention approach, adding telephone counseling to address barriers to physical activity (Step 2). Patients who still do not meet response criteria after Step 2 will progress to a more intensive Step 3, involving in-person PT visits. These visits will provide evaluation of functional impairments, further tailoring of exercises, and assessment of the need for devices that may also be needed to improve overall activity, as well as pain and function.

5.0 Theoretical Model of Physical Activity Behavior.

We have based STEP-KOA on Social Cognitive Theory (SCT; Figure 1) because of its comprehensive framework and its wide use in physical activity literature and other effective behavioral interventions for OA³⁷. SCT emphasizes that cognitive, behavioral, personal and environmental factors interact to influence motivation and

behavior. *Self-efficacy*, a central concept of SCT, is a powerful predictor of physical activity³⁸. Self-efficacy refers to one's belief in their ability to successfully complete a course of action, such as increasing physical activity. There are two types of self-efficacy that are important for physical activity behavior³⁹; *task self-efficacy* (e.g., exercise self-efficacy) is the belief that one can actually do the behaviors in question, and *barriers self-efficacy* is the belief that one can regularly perform a behavior in the face of common barriers such as lack of time, pain, etc. Each component of STEP-KOA addresses both types of self-efficacy. A second central concept of SCT is that of *outcome expectations*, defined as the anticipated results of a given behavior such as physical activity. SCT posits that individuals are more likely to engage in if they believe it will result in positive changes to valued outcomes (e.g. pain relief)⁴⁰. Each component of STEP-KOA also addresses outcome expectations. Overall, STEP-KOA provides augmented strategies for addressing SCT constructs for patients who do not have a clinically meaningful response to earlier steps.

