- STEP-KOA combines different strategies for improving physical activity, with an increase in the intensiveness of the approach for patients who do not meet benchmarks for improvement. This holds advantages over a “one-size-fits-all” approach, where individual patients may or may not achieve improvement with a given intervention. STEP-KOA modulates intervention intensity to meet patients’ needs.
- Step 1 can be administered widely at relatively low cost, and Step 2 is also a less costly approach to in-person PT visits (Step 3). Implementation of Steps 1 and 2 could therefore allow the VA to focus outpatient PT costs toward Veterans who fail to achieve clinically relevant improvement with lower cost exercise-related interventions. In addition, the goal of Specific Aim #3 is to describe patient characteristics associated with success in a low-resource intervention (Steps 1 or 2) vs. a need for more intensive or in-person care. This information has the potential to ultimately guide referrals to PT or other exercise-related care for knee OA. For example, if we find that participants who are older or who have worse baseline pain, functional limitations or general self-rated health are highly likely to progress to Step 3, these individuals could be targeted by the VA for PT referrals, which are most likely to meet their needs; conversely, patients who are younger and have better health and fewer symptoms could be steered toward beginning with the Step 1 program.
- If effective, STEP-KOA could serve as a model for other chronic conditions for which exercise and PT are key treatment components (e.g., low back pain).

C. METHODS

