1.0 Study Design. This will be a randomized controlled trial with participants assigned to two groups: STEP-KOA and Arthritis Education (AE) (Figure 2). We chose AE as the control condition for two primary reasons. First, this is an active condition, which will allow all participants to receive an OA-related intervention immediately. This may improve satisfaction and retention of participants, and it will help to account for any effects due to simply participating in an active intervention (e.g., attention effects). Second, AE has been utilized as an effective, feasible control condition in a number of other studies of behavioral interventions for OA⁵²⁻⁵⁵. We will use a 2:1 randomization ratio (STEP-KOA: AE Control); this design gives us ample sample size to characterize the STEP-KOA process and to explore characteristics of responders and non-responders at each evaluation time point (Specific Aim #3). Randomization will be stratified by gender and study site to ensure groups are balanced in these respects, since there is potential for treatment effects to differ based on these characteristics. Measurement time points are shown in Figure 2. Three and six-month

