5.0 STEP-KOA Intervention

5.1 Overview_ We have chosen intervention Steps that are evidence-based and focus on enhancing physical activity but differ in the amount, type and mode of care provided. We have chosen three-month intervals for the Steps, based on prior research indicating this is an adequate time period to observe meaningful changes in pain and function⁶¹. All participants in STEP-KOA will continue to have access to the Step 1 program for the full nine-month intervention period, regardless of whether they progress to Steps 2 and 3. This is because VET-KOA may serve as a complementary resource to participants who go on to receive telephone counseling and in-person PT visits; this approach is similar to other stepped care interventions^{33,35}. Further, continued access to VET-KOA is of minimal cost and would be feasible for the VA to provide to Veterans on a longer term basis. Some participants who initially meet response criteria at the three-month assessment point (and therefore remain at Step 1) may regress by six months and no longer meet benchmarks when compared to baseline pain and function. Since these patients initially met response criteria after Step 1, one likely reason for regression is encountering barriers to maintaining activity. These patients will be advanced to the Step 2 intervention at the six-month time point, since the telephone counseling intervention is aimed at addressing multiple types of barriers (Figure 2); this approach is also similar to other stepped care interventions^{33,35}.

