7.8 Participant Characteristics Associated with Treatment Response. Specific Aim 3 will evaluate participant characteristics associated with treatment response and the need for intensification to Steps 2 and / or 3 (See Section C.8.3). We will focus on four *a priori* characteristics we believe have strong potential for predicting the need of intervention intensification: age, baseline self-reported pain and function (single items described above for the Responder Criteria), and baseline self-rated general health (excellent, very good, or good vs. fair or poor). We have selected these measures because they are single items that could be quickly and easily administered in a clinical setting to guide referral to a specific treatment most likely to meet patients' needs.

7.9 Additional Participant Characteristics. We will assess the following to describe the study sample: age, race / ethnicity, gender, household financial state, education level, work status marital status, body mass index, questions about internet and technology use, the Patient Activation Measure, , comorbid illnesses (Self-Administered Comorbidity Questionnaire)⁸¹, joints with OA (including designation of unilateral vs. bilateral knee OA), duration of OA symptoms, and documentation of variables to verify an OA diagnosis based on American College of Rheumatology Clinical Criteria (duration of morning stiffness, presence of bony tenderness and bony enlargement, crepitus).

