8.3. Secondary Analyses. Since the secondary outcomes, 30 second chair stand and 40 meter fast-paced walk, are continuous, longitudinally collected measures, we will use similar modeling procedures as those described above for WOMAC scores to assess between-group differences at 9-month follow-up. We will also examine Poisson or negative-binomial mixed models as a sensitivity analysis as these outcomes (particularly chair stands) can be skewed and assumption of a normal distribution may not be reasonable.

For Specific Aim 2, to examine the maintenance effects of STEP-KOA at the 15-month follow-up, we will add the 15-month outcomes and the 15-month time-point to the fixed effect portion of the model. As we will only be estimating the maintenance effects for participants randomized to the STEP-KOA arm, we will drop the treatment by time variables from the fixed effects. We will set up contrasts of model parameters to estimate the difference and associated 95% confidence intervals in outcomes between the 9-month and 15-month time points. Models will also be fit to estimate these differences for subgroups defined by the combination of steps received during the STEP-KOA program by adding variables to the fixed effects indicative of the steps received as well as their interactions with time.

For Specific Aim 3, we are interested in understanding the flow of responders and non-responders through the STEP-KOA intervention. Our goal is to determine whether there are patient-level factors, already known or easily determined in routine clinic visits, which could be used by providers (individually or in combination), to guide referral of patients to a Step that is most likely to meet their needs. We will first calculate proportions of responders and non-responders at each time point and describe responder patterns longitudinally. We will also calculate proportions of individuals who meet response criteria in the two-different way described in Section C.5.1. We will then examine characteristics associated with responder status at each time point, using multivariable logistic regression models. In these models, we will first focus on the four *a priori* patient characteristics: age, baseline pain and function, and baseline self-rated health, to avoid spurious statistical findings⁸⁵. Based on clinical experience, we believe these variables have potential to predict response, and they can be assessed easily and quickly, making them practical screening tools.

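### Aim 3's 6-month response model does not isolate who needs Step 3; one added full-arm model of qualifying for Step 3 would

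*Combined protocol and SAP*

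**What the plan says.** Specific Aim 3 is worded by Step: "To describe patients who are non-responders at each Step in the STEP-KOA group, and to examine patient characteristics associated with non-response". Section 7.8 describes its target as "participant characteristics associated with treatment response and the need for intensification to Steps 2 and / or 3" and refers to section C.8.3 for the analysis. Section B (Significance) gives an example of use: if certain patients "are highly likely to progress to Step 3, these individuals could be targeted by the VA for PT referrals". Section 8.3 states its own goal as finding factors "to guide referral of patients to a Step that is most likely to meet their needs".

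For Aim 3, section 8.3 then plans proportions of responders, a longitudinal description of response patterns, and this regression: "We will then examine characteristics associated with responder status at each time point, using multivariable logistic regression models". The predictors are age, baseline pain, baseline function and self-rated health. No analysis set is named for the models at each time point, and reaching Step 3 is not named as an outcome. Section C.1.0 also frames Aim 3 by time point: "explore characteristics of responders and non-responders at each evaluation time point".

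Two rules govern movement at month 6. Section A.4.0 says: "Patients who still do not meet response criteria after Step 2 will progress to a more intensive Step 3, involving in-person PT visits". Section 5.1 deals with Step 1 responders who no longer meet the criteria at six months: "These patients will be advanced to the Step 2 intervention at the six-month time point".

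**The concern.** Up to month 3, time point and Step coincide. Everyone in the STEP-KOA arm has had Step 1 only, so the 3-month model answers who fails Step 1 and who enters Step 2 at that point. After month 3 they separate. A 6-month non-responder may be a Step 2 failure bound for Step 3, or a Step 1 responder who has slipped back and is bound for Step 2. A model of 6-month response over the whole arm puts both in one outcome category.

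The coefficient is a proper estimate of the association with 6-month response. It is not the association with reaching Step 3, which is what the PT-referral example in section B would use. A predictor of Step 3 need could look weaker than it is, or be missed. The longitudinal description of patterns will show how many people reach Step 3, but it does not relate that to the four predictors.

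**Working it through.** **Inputs.** Section 8.5: 230 participants in STEP-KOA; about 154 expected in Step 2 and about 76 in Step 3; 20% attrition at 9 months. Section 5.1: about one third respond after Step 1 and a further third after Step 2. Section 8.1: two-sided 0.05. The documents give neither a regression rate for Step 1 responders nor effect sizes for the predictors, so those below are assumptions.

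**1. The plan's own flow.** 230 × 2/3 = 153.3 enter Step 2 and 230 × 1/3 = 76.7 enter Step 3. These agree with 154 and 76. The remaining 230 × 1/3 = 76.7 are Step 1 responders.

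**2. Composition of 6-month non-responders.** With a fraction r of Step 1 responders regressing, regressors number 76.7r and all 6-month non-responders number 76.7 + 76.7r. The share not going to Step 3 is r/(1 + r).

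| r (assumed) | Regressors | 6-month non-responders | Share not going to Step 3 |
|---|---|---|---|
| 0% | 0 | 77 | 0% |
| 10% | 8 | 84 | 9% |
| 20% | 15 | 92 | 17% |
| 30% | 23 | 100 | 23% |

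Six-month non-response and reaching Step 3 are the same outcome only if nobody regresses. Sections 5.1 and 8.5 both allow for regression.

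**3. Effect on the odds ratio.** The simulation uses one standard normal predictor. One third respond at Step 1, half of the rest respond at Step 2, and Step 1 responders hold their response with a stated probability. Each of these three events follows a logistic model in the predictor. Odds ratios come from 1,000,000 records and power from repeated trials of n = 230. The first three columns give the assumed odds ratios for response or for holding it; the last two give the resulting odds ratios per SD for non-response. Holding is 80%.

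| Step 1 | Step 2 | Holding | 6-month model | Reaching Step 3 |
|---|---|---|---|---|
| 2.0 | 1.0 | 1.0 | 0.84 | 0.72 |
| 2.0 | 1.0 | 2.0 | 0.73 | 0.73 |
| 1.5 | 1.5 | 1.0 | 0.68 | 0.60 |
| 1.5 | 1.5 | 1.5 | 0.62 | 0.60 |
| 1.0 | 1.5 | 1.0 | 0.76 | 0.74 |

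In the first row, power is about 23% for the 6-month model and about 60% for reaching Step 3, with simulation error of a few points. With the same effects, the 6-month odds ratio is 0.89 at 70% holding and 0.79 at 90%, while that for reaching Step 3 stays at 0.72 to 0.73.

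**4. Feasibility of a Step 3 model.** There are about 76 events in 230, or 76/4 = 19 per predictor. After 20% attrition there are about 61 events in 184, or 15 per predictor. For one predictor, SE(log OR per SD) = 1/√(n·p·(1 − p)) with p = 1/3, and the odds ratio detectable with 80% power is exp(2.80 × SE):

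- n = 230: SE = 0.140, detectable odds ratio 1.48.
- n = 184: SE = 0.156, detectable odds ratio 1.55.
- n = 184, with the predictor sharing 30% to 50% of its variance with the other three (assumed; SE divided by √(1 − R²)): 1.69 to 1.86.

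**The case against.** Much of Aim 3 is already covered. The 3-month model is the Step 1 analysis. Every 6-month non-responder is stepped up, either to Step 2 or to Step 3, so the 6-month model does describe need for some intensification at month 6. Section C.1.0 defines the exploration by time point, and 8.3 delivers that. The clearest call for a Step 3 outcome is an example in the Significance section. Aim 3 is descriptive and has no hypothesis. The largest gap needs a strong predictor that acts on Step 1 response and on nothing else; if it also predicts holding the response, the gap all but disappears. All of this stands, and it limits the priority of the point.

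What it does not remove is that 7.8 names need for Step 3 as part of Aim 3 and sends the reader to 8.3, where no model separates Step 3 from late entry to Step 2. Which simulated case applies cannot be known in advance.

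A reader might infer more than the documents support:

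- **That the time-point models are wrong.** They are valid for response at each time point.
- **That 8.3 contains no other regression.** It also plans mixed models for the secondary outcomes, count models as a sensitivity analysis, and Aim 2 models by steps received. The statement about a single kind of regression is true of Aim 3 only.
- **That no Step question is answered.** The Step 1 question is.
- **That 8.3 fixes a whole-arm 6-month model.** It names no analysis set, so models within a Step are also a possible reading. The comparison above applies to the whole-arm reading.

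**Conclusion.** The point holds in limited form. As written, the Aim 3 regressions do not isolate who reaches Step 3, although need for Step 3 is part of the aim's stated purpose. Under assumed regression of 10% to 30%, 9% to 23% of 6-month non-responders are bound for Step 2. The consequence for a predictor's odds ratio runs from negligible to material, depending on whether the predictor also governs holding a Step 1 response; the plan has no information on that. This is an improvement to a secondary, exploratory aim, of low to moderate priority. It has no bearing on the primary comparison.

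**What to change.** In section 8.3:

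1. Keep the models at each time point and state that each covers all STEP-KOA participants.
2. Add one full-arm logistic model with the same four predictors. Its outcome is qualifying for Step 3 at month 6, meaning non-response at both 3 and 6 months, whether or not PT was then received. Defining it by qualification avoids dependence on PT availability, which section 5.4 says changed at Greenville in February 2018. Name this model as the Aim 3 analysis of need for Step 3 or PT.
3. State how missed assessments are handled. A response at either visit settles the participant as not qualifying; cases still undetermined go to the multiple imputation already foreseen in 8.4.
4. A model of 6-month response among those who entered Step 2 at month 3 is optional. If fitted, label it exploratory and conditional on Step 1 non-response, and do not use it as the basis for PT referral.

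The cost is a few sentences, with the same data and no change to N. The downside is one more exploratory model with limited precision: the detectable odds ratio per SD is about 1.5, or 1.55 after 20% attrition, and larger if the predictors are correlated, as pain and function may be.

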7.10 Knee OA and Related Care During Study Period. We will assess use of treatments for knee OA at baseline and follow-up assessments, including pain medications, topical creams, knee braces, joint injections, and assistive devices. We will assess this via self-report, as well as using VA medical records to identify receipt of physical therapy for knee OA, participation in MOVE!, and prescription pain medication use. We may also examine Fee Basis files to more comprehensively assess care received outside the VA. We will not exclude participants who have new OA treatments during the study period. However, it is important to evaluate whether there are differences in these treatments across study groups. If differences are observed, we will conduct two types of sensitivity analyses: a.) participants who received specific treatments will be excluded from analyses, b.) the specific treatment (e.g., new MOVE! participation) will be included as a covariate in statistical models. In addition, if we find that $\geq 20\%$ of participants have a change in any given type of treatment, we will conduct a sensitivity analysis that removes these participants. Because of the drastic improvements typically associated with joint replacement surgery, participants having this surgery during the study period will not be included in analyses of WOMAC scores. However, since receipt of total joint replacement is also an important OA outcome, we will compare the proportions of participants in each study group who receive this surgery during the study period.

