7.11 Measures for Cost-Effectiveness Analysis

Intervention Costs. We will use a micro-costing approach to derive labor and equipment costs for the STEP-KOA intervention. Labor costs for Step 1 will include programmer time to maintain the website and phone calls for technical support. Labor costs for the Step 2 intervention will include the time needed to train the exercise counselor and to conduct the telephone calls; this time will include any required pre-call preparation, post-call activities, partial call completions, call attempts and callbacks. Labor costs for Step 3 will involve the therapist's time to complete in-person visits. Hourly wage + fringe benefit rates for personnel will be applied to the labor time to derive total labor costs. The equipment costs for Step 1 include ankle weight and therapy bands, as well as the Apple iPad Air 16GB (encrypted with FIPS 140-2) (Version 9.3.1 (13E238) with Mobile Broadband Access Calling Plan costs for a subset of participants. Equipment costs for Step 3 include any devices recommended by the physical therapist. Adaptations to the existing VET-KOA website for this project will be one-time study-related costs and not included in the intervention cost estimate. Total labor and equipment costs will be divided by the number of patients in the STEP-KOA arm to derive per-patient intervention cost. We note that costs will vary across participants, participants will not all receive the same Steps. We will report this variability but are primarily interested in the average cost per participant.

Patient Resource Utilization and Costs. The intervention may affect primary care and specialist outpatient visits for OA and outpatient pain medication use. To assess VA outpatient visits and VA prescribed pain medication use and costs we will utilize the outpatient extract and pharmacy data extracts from the *DSS Outpatient National Data Extract (NDE)*, and the *DSS NDE SAS Pharmacy Dataset*. Outpatient encounters will be categorized using clinic stop codes of interest, as well as a count of total encounters and total costs of OA-related outpatient care. We will also include fee basis OA-related outpatient care and costs of the same categories because these are of increasing importance to VAMCs.

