8.0 Data Analyses

8.1. General Considerations. Primary study analyses will be conducted on an intent-to-treat basis, with participants analyzed in the group to which they were assigned. Additional exploratory analyses focusing on more restrictive analytic cohorts (e.g., per protocol analysis) will be considered, to provide additional information about the impact of magnitude of exposure to the intervention. The main conclusions drawn from this trial will be based on the pre-specified primary and secondary hypotheses outlined below and will be tested with two-sided p-values at the standard 0.05 level unless noted otherwise. Statistical analyses will be performed using SAS for Windows (Version 9.2: SAS Institute, Cary, NC) and R (<http://www.R-project.org/>).

8.2. Primary Analysis (Specific Aim 1). The main study outcome, WOMAC, is a continuous measure collected at baseline, 3, 6, 9 and 15 months (STEP-KOA group only). For the primary hypothesis we will examine STEP-KOA effects at the 9-month assessment. We will use a linear mixed model (LMM) that accounts for the correlation between a participant's repeated outcome measurements over time. We will apply an unstructured covariance matrix to take into account the within-patient correlation between repeated measures. The fixed-effect portion of the model will have the form: $Y_{it} = \beta_0 + \beta_1 3\text{month} + \beta_2 6\text{month} + \beta_3 9\text{month} + \beta_4 \text{STEP-KOA} * 3\text{month} + \beta_5 \text{STEP-KOA} * 6\text{month} + \beta_6 \text{STEP-KOA} * 9\text{month}$, where Y_{it} is the WOMAC score for subject i at $t=0, 3, 6, \text{ and } 9\text{months}$. We will estimate the parameters in the model and set up contrasts for tests of hypotheses using the SAS procedure MIXED (Cary, NC). Specifically, for Hypothesis 1, we will test for a difference in mean WOMAC scores between the STEP-KOA and AE groups at 9-months by testing that $\beta_6=0$.

Time is coded in the model to fit a constrained longitudinal data model (cLDA), in which baseline WOMAC score is modeled as a dependent variable in conjunction with the constraint of a common baseline mean across treatment arms⁸³. For improvement in precision, the model will be adjusted for stratification variables⁸⁴.

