9.0 Economic Evaluation. The overall goal of Specific Aim #4 is to provide the VA with information about the value of the STEP-KOA program, from a cost effectiveness perspective. In addition to informing the VA regarding the overall average cost of STEP-KOA per patient, this evaluation will provide information on how much improvement in outcomes can be achieved for that cost. This information is important for evaluating the potential for downstream implementation of STEP-KOA under various assumptions about scale and scope. We will not evaluate differences in costs or cost effectiveness according to the number of Steps each participant received; rather this will be a simple approach that is consistent with using the VHA perspective and comparing total aggregated costs across the two study arms (STEP-KOA vs. AE) at the 9-month follow-up point. The analysis will begin with descriptive statistics of the cost and effectiveness (utility) data. We will examine each measure of effectiveness, WOMAC and mean QALY (and the scores on the different EQ-5D-5L attributes, such as pain/discomfort), using the general analytic procedures and time points described above for primary and secondary outcomes. We will calculate the incremental cost effectiveness ratio (ICER) of STEP-KOA compared to the AE control group, separately for WOMAC and QALYs. The ICER will be calculated as the difference in the average total cost per participant STEP-KOA and AE, divided by the difference in the average effectiveness per participant between STEP-KOA and AE. Bootstrapping of estimates, multiple imputation for missing EuroQoL values, and sensitivity analyses will all be conducted to ensure robustness of our results.

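### The ICER's cost difference is planned with no adjustment for OA-related cost before randomization, which gives up some precision but introduces no bias

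*Combined protocol and SAP*

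**What the plan says.** Section 9.0 (Economic Evaluation) takes the VHA perspective and describes a deliberately simple comparison: "comparing total aggregated costs across the two study arms (STEP-KOA vs. AE) at the 9-month follow-up point". The numerator of the ratio is set out as "The ICER will be calculated as the difference in the average total cost per participant STEP-KOA and AE". The denominator is worded in the same way, as a difference in average effectiveness. Effectiveness, however, has a further sentence: WOMAC and mean QALY are to be examined "using the general analytic procedures and time points described above for primary and secondary outcomes". Cost has no such sentence. On robustness the section says only: "Bootstrapping of estimates, multiple imputation for missing EuroQoL values, and sensitivity analyses will all be conducted to ensure robustness of our results".

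The procedures referred to are in Section 8.2, where "baseline WOMAC score is modeled as a dependent variable in conjunction with the constraint of a common baseline mean across treatment arms", and where the plan adds: "For improvement in precision, the model will be adjusted for stratification variables". Those variables are gender and site (Section 1.0).

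On data, Section 7.11 says: "To assess VA outpatient visits and VA prescribed pain medication use and costs we will utilize the outpatient extract and pharmacy data extracts", and adds fee basis outpatient care for OA. It gives no look-back window. Section 7.10 says: "We will assess use of treatments for knee OA at baseline and follow-up assessments", using self-report and VA records. No section uses pre-randomization data in the cost analysis.

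**The concern.** The plan uses baseline information to sharpen the WOMAC comparison and relies on that gain in its sample size, but does nothing comparable for cost. If OA-related cost before randomization predicts such cost afterwards, a chance difference in prior use between 230 STEP-KOA and 115 AE participants carries partly into the unadjusted cost difference, and the interval is wider than it needs to be. Aim 4 is meant to inform VA implementation, so the precision of the cost difference matters. If adjustment is left open, the choice between an adjusted and an unadjusted ratio could also be made after the results are seen.

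**Working it through.** **The plan's own figure and variance factor.** Section 8.5 gives a difference of 5.8 points, SD 17.5, correlation 0.4, two-sided alpha 0.05, power 80%, 2:1 allocation and 20% attrition. It multiplies the two-sample size by 1 − ρ².

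- AE arm before adjustment: 1.5 × (17.5 × (1.960 + 0.842) / 5.8)² = 107.2
- Times 1 − 0.4² = 0.84: 90.0
- Divided by 0.80: 112.5 AE, 337.6 in total
- With 0.33 SD (5.775 points) instead: 113.5 AE, 340.6 in total

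The plan states 115 and 345, so its figure reproduces within 3%. It is not affected by this point.

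**The same factor applied to cost.** The SE of a raw difference in means is SD × √(1/230 + 1/115) = 0.1142 SD. Linear adjustment for prior cost multiplies it by √(1 − ρ²), where ρ is the correlation between prior and follow-up OA-related cost. The chance prior-cost difference that carries into the raw estimate has SD ρ × 0.1142 SD, so its 95% range is ±1.96 × ρ × 0.1142 SD. The documents give no ρ or SD for cost, so ρ is assumed over a range and results are in SD units.

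| Assumed ρ | SE ratio √(1 − ρ²) | Interval narrows by | 95% range of carry-over |
|---|---|---|---|
| 0.1 | 0.995 | 0.5% | ±0.022 SD |
| 0.2 | 0.980 | 2.0% | ±0.045 SD |
| 0.3 | 0.954 | 4.6% | ±0.067 SD |
| 0.4 | 0.917 | 8.3% | ±0.090 SD |
| 0.5 | 0.866 | 13.4% | ±0.112 SD |
| 0.6 | 0.800 | 20.0% | ±0.134 SD |
| 0.7 | 0.714 | 28.6% | ±0.157 SD |

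At ρ = 0.4 (the plan's WOMAC value, borrowed only for illustration) the variance falls by 16%. That equals an unadjusted trial of 345 / 0.84 ≈ 411.

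**Skewed costs.** A simulation with lognormal costs (log-SD 1.2, 230 + 115, 5,000 runs, no true difference) gave SE ratios of 0.976, 0.885 and 0.761 at ρ = 0.2, 0.4 and 0.6. Both estimators were centred on zero. In that setting skewness did not remove the gain, and the raw difference was not biased.

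**Effect on the ratio.** With 184 + 92 completers, the WOMAC difference has SE 17.5 × √0.84 × √(1/184 + 1/92) = 17.5 × 0.9165 × 0.1277 = 2.05, which is 2.05 / 5.8 = 35% of the target difference. For illustration only, assume a cost SD of $1,000–2,500 (SE $114–286 with 230 + 115), a cost difference of $500–1,000, ρ = 0.5 and no covariance between cost and effect. The approximate relative SE of the ratio is the root of the two squared relative SEs summed.

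- SE $114, difference $1,000: √(0.114² + 0.353²) = 0.371 raw; √(0.75 × 0.114² + 0.353²) = 0.367 adjusted; about 1% lower
- SE $286, difference $500: √(0.572² + 0.353²) = 0.672 raw; √(0.75 × 0.572² + 0.353²) = 0.608 adjusted; about 10% lower

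Both are below the 13% gain in the cost difference alone.

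**The case against.** The strongest reply is that nothing here is wrong. A raw difference in mean cost is a valid estimator in a randomized trial, the bootstrap carries its chance variation into the interval, and Section 9.0 openly chooses simplicity. All of that stands. It does not remove the precision gain, which rests on the logic the plan applies to WOMAC.

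Section 9.0 is also silent on adjustment and does not exclude it; the unspecified sensitivity analyses could include it. That is so, but an unspecified analysis is not a pre-specified estimator.

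The size is uncertain and may be trivial. At a correlation of 0.1–0.2 the interval narrows by only 0.5–2%. The utilization costs listed in Section 7.11 are OA-related outpatient visits and pain medication, so general experience of very variable health care cost need not transfer. The intervention cost is an average over the STEP-KOA arm, which prior cost would not change. Randomization is already stratified by gender and site, so adding them does little about imbalance.

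Two stronger readings are tempting. A reader might infer that chance imbalance could match or exceed the cost of the program itself. The documents list the program's cost components but give no dollar amounts, so that comparison has no basis. A reader might also infer that prior cost is available for every participant. Routine VA extracts and pre-enrollment record review make earlier data likely, but no section states a pre-randomization window or complete coverage.

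**Conclusion.** The point holds as a modest, optional improvement. Section 9.0 defines the cost numerator as a difference in arm averages with no adjustment for pre-randomization cost, while WOMAC and QALYs go through the baseline-adjusted procedures. The consequence is lost precision and uncorrected chance imbalance in the utilization part of cost. It should not be read as bias.

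The interval for the utilization cost difference would narrow by about 0.5% to 29% over assumed correlations of 0.1 to 0.7. The gain is negligible at 0.1–0.2 and becomes material from about 0.4. The gain in the ratio is smaller: roughly 1–10% at a correlation of 0.5 under the illustrative dollar assumptions. The size depends on a cost correlation, and for the ratio also on a cost SD and a cost difference, that the documents do not give.

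**What to change.** Add to Sections 7.11 and 9.0:

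- Extract OA-related outpatient and pain-medication cost from the same DSS and fee basis sources for a fixed window before randomization, for example 9 months. State how participants with no VA records in that window are handled.
- Estimate the STEP-KOA minus AE cost difference by regression on arm, prior OA-related cost, gender and site, within the same bootstrap replicates as the effect difference.
- Report the raw difference in means beside it, and say in advance which of the two enters the main ratio.

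The cost is a longer date range in an extraction already planned and a few lines of SAP text. The downside is that the look-back must fall within the approved data request, which may need extending.
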